#### 4.1 SUBJECT DISPOSITION

Subject disposition will be summarized by treatment group and by all randomized subjects. The summary will include

number of subjects randomized

- number of subjects completed the study
- number of subjects discontinued from the study.

Reasons for discontinuation will be summarized by randomized treatment group for all randomized subjects. Table 14.1.1 provides the subject disposition for all screened subjects.

Listing 16.2.1.1 provides screen failures for all screened subjects. Listing 16.2.1.2 provides subject disposition for all randomized subjects.

### 4.2 ANALYSIS POPULATIONS

The population of "All Screened Subjects" will contain all those subjects who entered the screening period to determine their eligibility to participate in the study.

The population of "All Randomized Subjects" will contain all those screened subjects who meet the requirements for study participation and are randomized, using a centralized randomization system, to either SPN-812V or placebo.

The "Intent-to-Treat (ITT) Population" consists of all randomized subjects who took at least one dose of SM, had baseline efficacy assessment and had at least one post-baseline efficacy assessment. The ITT population is the primary population for the efficacy analysis.

The "Restricted ITT Population" consists of all ITT population subjects with at least 1 efficacy assessment after three weeks of treatment.

The ITT and Restricted ITT populations will be analyzed according to treatment assigned. All subjects randomized to SPN-812V 300mg/day group, whether they are maintained on 300mg or reduced to 150mg, will be analyzed under the SPN-812V 300mg/day group.

The "Safety Population" consists of all randomized subjects who receive at least 1 dose of SM.

The PK population consists of all safety subjects who consented to participate in the optional PK sub study and had at least one evaluable (non-BLQ) PK sample drawn.

The safety and PK populations are based on actual treatment received.

Table 14.1.2 provides these analysis populations for all randomized subjects.

Listing 16.2.2 provides inclusion and exclusion criteria violations for all randomized subjects. Listing 16.2.3 gives analysis populations.

### 4.3 DEMOGRAPHICS AND BASELINE CHARACTERISTICS

Subject demographic and baseline characteristics data will be summarized by treatment group for the safety, ITT, and restricted ITT populations.

Demographic information (Sex, Race, Ethnicity and Age) will be listed (Listing 16.2.4). Height, weight and BMI will be listed with vital signs (Listing 16.2.9) where height is measured at screening only. Descriptive statistics will be obtained for the continuous variables: age, height, weight and BMI (Table 14.1.3.1.1 through 14.1.3.1.3). Frequencies and percentage of subjects will be tabulated for the categorical variables: sex, race and

ethnicity (Table 14.1.3.2.1 through 14.1.3.2.3).

To calculate age, the following formula will be used:

Age (years) = INT { (date of screening – date of birth) / 365.25 }.

#### 4.4 **MEDICAL AND PSYCHIATRIC HISTORY**

Medical and psychiatric history data recorded prior to dosing will be listed by subject for the safety population. Only those body systems where a condition or abnormality has been reported will be listed (Listing 16.2.5.1 and 16.2.5.2).

The diagnoses present in subjects' medical history and the duration of those medical conditions will be presented by treatment group in Table 14.1.3.3. If start date is incomplete or missing, date of informed consent will be used for imputing the duration.

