## 9.1.1. Screening Period

Screening will take place within 14 days prior to randomization to determine subjects' eligibility to participate in the study. No screening or study-specific assessments may be performed until written informed consent has been obtained. Screening procedures will be performed to determine each subject's eligibility to participate in the study and may be carried out over more than one visit during the Screening Period. Abnormal results on laboratory tests may be repeated once at the discretion of the Investigator during the Screening Period.

Additional screening procedures will include review of medical and psychiatric history, including confirmation of ADHD diagnosis and smoking history; assessment of suicide risk; assessment of demographic and baseline characteristics; full physical examination; measurement of vital signs, height and weight; ECG; sample collections for hematology, biochemistry, CYP2D6 enzyme activity screening, urinalysis, urine drug screen and serum pregnancy test (FOCP only); prior and concomitant medication information will also be collected.

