#### 9.7.1.1.1. Demographic/Baseline Analyses

Demographic/baseline variables include age, sex, ethnicity, race, baseline height, baseline weight, and medical history. Tabular summaries of the demographic/baseline variables will be presented for the safety, ITT, and restricted ITT populations, except for medical history, which will be summarized for the safety population only.

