### 3. DESIGN OF THE STUDY

### 3.1 STUDY DESIGN

This will be a multicenter, randomized, double-blind, placebo-controlled, parallel group study of the safety and efficacy of SPN-812V in adults with ADHD. The target subjects are male or female adults aged 18 to 64 years, inclusive, with a diagnosis of ADHD. A total of fifty subjects will be enrolled at approximately 5 sites in the US. Subjects will be randomized (1:1) to one of two treatment groups, SPN-812V or placebo.

The study will consist of a Screening Period (within 14 days prior to randomization) and a Dosing Period of 6 weeks. The total subject duration in the study will be up to 8 weeks as illustrated in Figure 1.

[figure not shown]

Figure 1 Study Schematic

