### 3.1.1 Screening

Screening will take place within 14 days prior to randomization to determine subjects' eligibility to participate in the study. Screening procedures will be performed to determine each subject's eligibility to participate in the study and may be carried out over more than one visit during the Screening Period.

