### 3.1.2 Dosing Period

Subjects who meet the requirements for study participation will be randomized and proceed to the Dosing Period which will last 6 weeks. Approximately 50 subjects will be randomized at a 1:1 ratio, using a centralized randomization system, to either SPN-812V or placebo. The first dose of SM should be taken the morning after the randomization visit. Subjects who do not tolerate the starting dose will be discontinued from the study.

The first dose of SM should be taken the morning after the randomization visit. Subjects will receive treatment at the 150 mg/day starting dose for one week. Subjects who do not tolerate the starting dose will be discontinued from the study.

Subjects who tolerated the starting dose will then be titrated to receive a study dose of 2x50 mg TID (300mg/day) and continue this treatment regimen for five weeks. Subjects who, after titration to the study dose, do not tolerate treatment at 300 mg/day, will be allowed, at any time, to down-titrate the dose to the 150 mg/day starting dose and continue treatment at the same dose until completion of the study. Subjects will return to the investigational site once a week to undergo safety and efficacy evaluations and to have SM compliance checked.

Subjects who have consented to participate in the optional PK sub study will be given a diary at Visit 7 on which to record time of SM doses taken prior to Visit 8. Subjects who are participating in the optional PK sub study will be given all efficacy assessments prior to blood draws or dosing on the PK day. For subjects not participating in the optional PK sub study, their last dose will be taken the evening before the End of Study Visit (Visit 8).

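### SAP 4.4 imputes the duration of a medical condition from the consent date even when the start year is recorded, so durations in Table 14.1.3.3 are understated

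*SAP*

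**What the plan says.** SAP 4.4 plans a listing and a table of medical history. The listing covers what is known before treatment: "Medical and psychiatric history data recorded prior to dosing will be listed by subject for the safety population". For the table, it says that "the duration of those medical conditions will be presented by treatment group in Table 14.1.3.3". The rule for imperfect dates is a single sentence: "If start date is incomplete or missing, date of informed consent will be used for imputing the duration".

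SAP 4.4 has no separate rule for a date with a known year or month, and it does not say to which date the duration runs. Protocol 9.7.1.1.1 makes medical history part of the baseline description: "Demographic/baseline variables include age, sex, ethnicity, race, baseline height, baseline weight, and medical history". It limits the medical-history summary to the safety population and does not mention duration, which is an addition in the SAP.

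No other section overrides the rule. SAP 5.1.6 deals with efficacy scores and missing scale items. SAP 6.1.1 deals with missing information on adverse events. SAP 4.7 names missing data as a topic for the blind data review but gives no rule for partial dates.

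**The concern.** Incomplete and missing are different states. If the year is recorded, the duration of a condition is known to within about a year. Replacing that date with the consent date turns a nearly known value into one that contradicts the case report form. For any condition already present at consent, consent is the latest possible start, so the error runs only towards a shorter duration.

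What is at stake is whether the reported durations can be read. SAP 4 summarises continuous variables by mean, standard deviation, median, minimum and maximum. If artificial values near zero are mixed with real durations, a reader cannot tell a recent condition from a poorly dated one. Resolved conditions could add negative values.

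**Working it through.** The plan gives no figure to reproduce, so the check is date arithmetic.

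**Inputs from the documents**
- Consent comes first (Protocol 9.1.1): "No screening or study-specific assessments may be performed until written informed consent has been obtained". The visit schedule places it at Visit 1.
- Consent to randomization is at most 14 days (SAP 3.1.1): "Screening will take place within 14 days prior to randomization to determine subjects' eligibility to participate in the study".
- First dose (SAP 3.1.2): "The first dose of SM should be taken the morning after the randomization visit". This is about day 15 at the latest.
- Longest time in study (SAP 3.1): "The total subject duration in the study will be up to 8 weeks as illustrated in Figure 1". This is 8 × 7 = 56 days.

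**Assumptions, for illustration only**
- Consent on 1 September 2010.
- A true mean duration of 10 years.
- A share p of conditions with incomplete dates of 10%, 30% or 50%.

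**Step 1: duration under the SAP rule, ongoing condition.** Duration = end date − consent date.

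| End date chosen | Days | Years (days / 365.25) |
|---|---|---|
| Consent | 0 | 0.00 |
| Visit 2 | at most 14 | 0.04 |
| First dose | about 15 | 0.04 |
| End of study | at most 56 | 0.15 |

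The result is close to zero whichever end date is chosen.

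**Step 2: what a recorded year already tells us.** The true duration to consent lies between consent − 31 December and consent − 1 January of the recorded year.

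| Recorded year | True range (years) | With 1 July imputed | SAP rule, to consent |
|---|---|---|---|
| 2009 | 0.67 to 1.66 | 1.17 | 0 |
| 2005 | 4.67 to 5.66 | 5.17 | 0 |
| 1990 | 19.67 to 20.67 | 20.17 | 0 |

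Imputing 1 July is wrong by at most about 0.5 year. The SAP rule loses the whole duration, which is little for recent onset and about 20 years for a condition dating from 1990.

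**Step 3: resolved conditions.** Suppose the duration is counted to a recorded end of 30 June 2008 and the start is set to 1 September 2010. The duration is then −2.17 years.

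**Step 4: effect on a mean.** Setting affected records to zero, and assuming that duration is unrelated to completeness:

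reported mean = (1 − p) × true mean + p × 0

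- p = 10%: 0.9 × 10 = 9 years
- p = 30%: 0.7 × 10 = 7 years
- p = 50%: 0.5 × 10 = 5 years

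If older conditions are more often incompletely dated, the proportional loss exceeds p. If recent ones are, it is smaller. The documents do not say which applies.

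**The case against.** The strongest reply is about wording. The SAP uses the consent date to impute the duration; it does not literally say that the start date becomes the consent date. For a partial date, a programmer might take only the missing day and month from consent and keep the year. The text neither states nor excludes this. However, it cannot work for a wholly missing date, which the same sentence covers, so plain substitution is the natural reading. If the milder reading was meant, the sentence still needs rewriting.

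Two stronger readings are tempting, and the documents support neither.
- A reader might infer that most long-standing conditions are dated by year only, so that the table would show a population with mainly new conditions. Nothing in the documents gives the share of incomplete dates. It depends on the eCRF screens and database specifications that SAP 1 lists, which are not part of these documents.
- A reader might infer that the arms or sites are no longer comparable. History is taken at screening (SAP 3.6.4), before 1:1 randomization at Visit 2, so completeness cannot depend on the assigned arm and any difference between arms is chance. No site comparison is planned: SAP 4 combines the sites and SAP 5.1.3 pools the centers.

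It is also fair to say that little hangs on this number. The duration is not an endpoint, an eligibility criterion, a subgroup factor or a term in the repeated-measures model. SAP 4 lists all eCRF data, so the recorded dates should remain visible there. The blind data review in SAP 4.7 gives an opportunity to correct the rule before lock, although it does not commit to doing so.

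**Conclusion.** The point holds as a minor one. As written, and on its natural reading, SAP 4.4 discards recorded years and months. It gives ongoing conditions a duration of 0 to 56 days, and conditions that resolved before consent a negative one when counted to their recorded end. Durations in Table 14.1.3.3 are understated whenever a start date is incomplete.

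The overall size cannot be stated from the documents. A cut in the mean of about p rests on two assumptions: the value of p, and no relation between duration and completeness. The percentages above are illustrations, not estimates for this trial.

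The consequence ends at one descriptive table. No efficacy or safety comparison is affected, and no bias between arms is expected.

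**What to change.** Replace the imputation sentence in SAP 4.4 with a rule that does the following:
- Keeps every recorded part of the start date and imputes only what is missing: for example the 15th if only the day is missing, and 1 July if day and month are missing. In both cases the imputed date is capped at the consent date and, for a resolved condition, at its recorded end if that is earlier.
- Leaves the duration missing if the year is missing, and reports the number missing in Table 14.1.3.3.
- Defines the end of the duration: for example the consent date for ongoing conditions and the recorded end date for resolved ones.

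The 15th and 1 July are conventions. Any stated choice that keeps the recorded year would serve.

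The cost is a few sentences in the SAP and one derivation, with no new data collection provided the eCRF already holds end dates for resolved conditions. The change can be agreed at the blind data review before lock. After lock it would go into the addendum that SAP 8 describes.

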#### 4.5 TREATMENT COMPLIANCE AND EXPOSURE

Tabular summaries of the compliance rate and duration of treatment exposure to SM will be presented for the safety population by treatment group. Summary of treatment compliance and exposure will be provided separately for the first week of start-up dose (Baseline and Randomization Period), study maintenance dose period (Study Dose Treatment Phase), and combined Baseline and Randomization and Study Dose Treatment Phase (Table 14.1.4.1). Listing 16.2.5.3 provides the compliance data.

The number and percentage of subjects maintained on the target dose (300mg) versus those reduced in dose (150mg) during the Study Dose Treatment Phase will be provided (Table 14.1.4.2).

#### 4.6 POTENTIAL EXCLUSIONS FROM ITT POPULATION

Study data will be examined during the Blind Data Review (described below in section 4.7) for potential exclusions from ITT population. ICH E9 guideline outlines circumstances where it will usually be acceptable to omit subjects from the ITT population without causing bias. Some of the potential exclusions in this study are:

- Subjects who violate the inclusion/exclusion criteria;
- Subjects who fail to take at least one dose of study medication;
- Subjects who do not provide any post-baseline data;
- Enrollment of a subject who did not meet all inclusion/exclusion criteria which would affect subject safety or would negatively impact data integrity;
- Use of any prohibited concomitant medication that may confound study results;
- Subject dosing error that results in a serious adverse event;
- Having any non-compliance issues raised by the investigator or sponsor prior to breaking the blind;
- Study visit or procedure conducted outside of required time frame that may negatively affect subject safety;
- Subject visit/procedure falls outside of the window of time indicated by the protocol

resulting in increased potential for risk to the subject or any damage to the integrity or completeness of the data.

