### 9.7.1.1. Analysis Populations

The safety population consists of all randomized subjects who take at least one dose of SM.

The intent-to-treat (ITT) population consists of all randomized subjects who took at least one dose of SM (i.e., the safety population), had baseline efficacy assessment, and had at least one post-baseline efficacy assessment.

The ITT population is the population for the efficacy analysis. Subjects will be analyzed according to treatment assigned.

The restricted ITT population consists of all ITT population subjects with at least 1 efficacy assessment after three weeks of treatment.

The PK population consists of all Safety population subjects with an evaluable PK profile.

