#### **10.4.** Adherence to the Protocol

The Investigator will conduct the study in strict accordance with the protocol, which has been written to enable the Investigator's compliance with ICH E6, Section 4, "Investigator Guideline for Good Clinical Practices".

There are to be no Investigator-initiated deviations from the protocol. Any subject whose treatment deviates from the protocol or who is not qualified for study participation may be ineligible for analysis and may compromise the study. On occasion, a subject whose medical condition does not exactly conform to the specifications of the protocol but who could potentially benefit from study participation may be considered for enrollment by the Sponsor if the Investigator first reviews the situation with the Medical Monitor. In these cases, the potential subject's participation will be discussed with the Sponsor personnel prior to having the subject sign the informed consent, and the exemption for study enrollment will be sent in writing to the investigational site by the Sponsor. The investigational site will retain a copy of this document. If the Investigator learns at any time after informed consent that a subject does not meet protocol specifications for study participation, he/she will call the Medical Monitor immediately.

Subjects who have not signed an IRB approved ICF cannot receive SM.

The Investigator and research team must comply with ICH E6 principles and all applicable local regulatory laws and regulations.

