#### 4.7 **BLIND DATA REVIEW**

The checking and assessment of data to revisit the proposed methods of statistical analysis for the purpose of finalizing the planned analysis prior to the database lock will be conducted. The following lists some of the aspects of analysis that would be considered:

- Checking of data for potential exclusions from ITT population;
- Precise definitions of analysis populations, especially which subjects will be included and which will be excluded;
- Handling of missing data;
- Outlier identification and specific decisions taken on how these will be handled.

The data review will be documented in agreed and signed meeting minutes, which will include a version of Listing 16.2.3 as appendix. The blind data review meeting minutes will be included in Appendix 13.1.

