#### 5.1.2 **Treatment Comparisons**

Statistical testing to compare treatment groups will be performed for the ITT population only using appropriate statistical methods, as described in the efficacy subsections below. Given the small per-treatment group sample size for the study, the resulting p-values from the statistical testing will be used for descriptive purposes only (i.e., not for inferential purposes), primarily as an aid in the clinical interpretation of the efficacy results.

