#### 5.3.2 Global Improvement (CGI-I)

Actual CGI-I scores at each post-baseline visit and endpoint will be compared among treatment groups using two-sample t-test if normality assumption is satisfied.

In case of non-normality of scores, Wilcoxon rank-sum test will be used. The Hodges-Lehmann estimate and associated 95% confidence interval will be calculated for the median difference between treatments.

Tables 14.2.2.2.1 and 14.2.2.2.2 provide secondary efficacy results for CGI-I for the ITT and restricted ITT populations. Tables 14.2.2.2.3 and 14.2.2.2.4 provide the number and percentage of subjects with CGI-I < 3 at the end of study (EOS) for the two treatment groups for the ITT and restricted ITT populations respectively. Listing 16.2.6.2.1 provides CGI-S and CGI-I data for the ITT population.

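### SAP 4.6 and 4.7 let subjects who meet the ITT definition be dropped on open-ended grounds, so a selectively reduced efficacy estimate could still be labelled ITT

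*SAP*

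**What the plan says.** Protocol 9.7.1.1 and SAP 4.2 agree on who is in ITT: randomised subjects who took at least one dose and, in the SAP's words, "had baseline efficacy assessment and had at least one post-baseline efficacy assessment". The protocol adds: "The ITT population is the population for the efficacy analysis. Subjects will be analyzed according to treatment assigned". Neither definition mentions compliance, eligibility, concomitant medication or visit timing.

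SAP 4.6 then lists grounds for leaving subjects out of ITT, introduced by "Some of the potential exclusions in this study are". Two bullets (no dose, no post-baseline data) only restate the definition. The others can remove a subject who satisfies it:

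- any eligibility violation (a second bullet limits this to violations that bear on safety or data integrity, but the first bullet has no such limit);
- prohibited medication that might confound the results;
- a dosing error that leads to an SAE;
- "Having any non-compliance issues raised by the investigator or sponsor prior to breaking the blind";
- visits or procedures outside their time frame, where safety or data integrity may suffer.

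SAP 4.7 leaves to the blind review "Precise definitions of analysis populations, especially which subjects will be included and which will be excluded", along with missing-data handling and outliers. The review takes place before database lock and is recorded in signed minutes with a version of Listing 16.2.3.

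Protocol 10.4 says that deviating or unqualified subjects "may be ineligible for analysis and may compromise the study". It names no population and gives no criteria.

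**The concern.** A reader of the study report will take ITT to mean the SAP 4.2 population. Under SAP 4.6 and 4.7 it could instead be that population minus subjects chosen at a meeting, on grounds that are partly open and partly matters of judgement. Missed doses, prohibited medication and late visits happen after randomisation and may follow from poor tolerability or lack of effect, either of which can differ between active and placebo. Eligibility violations mostly concern status before randomisation and are the weakest part of the case.

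If exclusions differ by arm in a way related to outcome, the CAARS and CGI-I contrasts move towards a per-protocol comparison while keeping the ITT label. No planned analysis would show this. The restricted ITT set is a subset of ITT (SAP 4.2), and the MMRM sensitivity analysis is run on ITT (SAP 5.4). No per-protocol set is defined, and no analysis of the unreduced set is specified. The minutes and the listing would show who was removed, but not what the estimate would have been with them included.

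**Working it through.** **Text.** The two definitions were set against each ground in SAP 4.6, as above. Apart from the two restating bullets, each ground can remove a subject who meets SAP 4.2. SAP 8, headed as changes from the protocol, does not record this as a departure. Two other places pull the opposite way. Protocol 10.4 lets the sponsor exempt a non-conforming subject in writing before enrolment, and SAP 4.6 could then drop that subject as an eligibility violator. Protocol 9.4.5 asks investigators to retain subjects after a remediable lapse in compliance, and SAP 4.6 could then drop them for non-compliance.

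**The plan's own figure.** The documents give no power, effect size or SD. The one checkable figure is the number of completers: 50 × (1 − 0.20) = 40, as stated in protocol 9.2.

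**Inputs.** 25 per arm (protocol 9.7.2, SAP 3.2); tests at the 0.05 level (SAP 5), taken as two-sided. Assumptions: unit-SD normal change scores, no true effect, k subjects excluded per arm.

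**Standard error of the difference** with nobody excluded: √(2/25) = 0.283 SD.

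**Scenario A.** Active exclusions fall at random within the poorer-responding half; placebo exclusions are fully random. The retained active mean shifts by k × m / (25 − k), where m is the expected mean of the poorer half: 0.742 SD if that is the worst 13 of 25, 0.804 SD if the worst 12. For k = 3: 3 × 0.742 / 22 = 0.101 and 3 × 0.804 / 22 = 0.110. For k = 5: 5 × 0.742 / 20 = 0.186 and 5 × 0.804 / 20 = 0.201. A simulation of 100,000 null trials agrees:

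| Excluded per arm | Bias favouring active (SD) | Bias / 0.283 | Null rejection |
|---|---|---|---|
| 0 | 0 | 0 | 5.0% |
| 1 | 0.031–0.033 | 0.11–0.12 | 4.9–5.0% |
| 2 | 0.065–0.069 | 0.23–0.24 | 5.2–5.4% |
| 3 | 0.102–0.111 | 0.36–0.39 | 5.9–6.2% |
| 5 | 0.187–0.200 | 0.66–0.71 | 8.2–9.1% |

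With the same selection in both arms, bias is 0.00 for every k, and rejection is 4.6–4.8% at k = 1 and 3.9–4.1% at k = 5.

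**Scenario B, a different mechanism.** Subjects with the highest non-compliance score are removed, and the score has correlation 0.3 to 0.5 with poor outcome (40,000 null trials):

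| Removed, active vs placebo | Bias favouring active (SD) | Null rejection |
|---|---|---|
| 3 vs 3 | about 0 | 5.0–5.7% |
| 3 vs 1 | 0.04–0.07 | 5.4–6.2% |
| 5 vs 1 | 0.08–0.13 | 5.8–7.6% |
| 5 vs 0 | 0.10–0.17 | 6.4–8.9% |

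With correlation 0, bias is nil and rejection is about 5% in every case.

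**Reach of the timing ground.** If each of the 6 weekly visits has an assumed 2%, 5% or 10% chance of falling outside the ±2-day window, then 1 − (1 − q)^6 = 11%, 26% or 47% of subjects have at least one such visit (about 6, 13 or 23 of 50). This is an upper bound, because the bullet also requires added risk to the subject or damage to the data.

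**The case against.** The exclusions are only potential. The review is blind, precedes lock and is minuted. The investigator and sponsor, who may raise compliance issues, are both blinded (protocol 9.5.4 and 9.5.9). Table 14.1.2 reports the populations for all randomised subjects, so a reduction would be visible. The larger biases need an asymmetry for which the documents offer no evidence, and five exclusions per arm would discard 20% of the trial. With one or two per arm the shift is at most about a quarter of a standard error. Efficacy is a secondary objective and its p-values are descriptive (SAP 5.1.2), so null rejection rates are a side measure. Protocol 10.4 is permissive conduct language; if it has analytic force, it suggests that the protocol itself foresaw exclusions.

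Most of this stands as a limit on likelihood and size. It does not close the gap. Visibility is not an estimate on the full set, and blinding cannot prevent selection that works through tolerability or lack of effect. Dosing records are also kept by unblinded site staff (protocol 9.5.11), so the source of a compliance issue may not be fully blind. SAP 4.6 appeals to ICH E9 for omissions that cause no bias, but does not show that each listed ground qualifies. Descriptive p-values do not help either, since the estimate and its interval are what a proof-of-concept trial delivers. The protocol 10.4 point is minor, and the main finding does not depend on it.

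**Conclusion.** The concern holds and should be fixed. Followed as written, the SAP can produce a selectively reduced efficacy set that is reported as ITT, with no planned analysis on the population that SAP 4.2 defines. That conclusion rests on the text and is firm.

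The amount of bias is conditional. It is nil without exclusions or with like selection in both arms, small for one or two exclusions per arm, and up to about 0.2 SD (0.7 of a standard error) for five per arm under one-sided selection. The exclusion counts, the selection mechanism and its direction are all assumptions, because the documents give none of them. The harm falls mainly on the CAARS and CGI-I estimates and their intervals. The primary safety analysis uses a population to which SAP 4.6 does not apply.

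**What to change.** - In SAP 4.6 and 4.7, state that ITT is exactly the SAP 4.2 population and that no other ground removes a subject.
- Move the remaining grounds to a separately named per-protocol set with closed, objective criteria (for example, a numeric compliance threshold), fixed before the scores are reviewed and used only for a supplementary analysis.
- Keep the tables now assigned to ITT on that population (including 14.2.1.1, 14.2.2.1, 14.2.2.2.1, 14.2.2.2.3, 14.2.2.3.1, 14.2.2.4 and 14.2.3). Leave the restricted ITT tables (14.2.1.2, 14.2.2.2.2, 14.2.2.2.4 and 14.2.2.3.2) as assigned, but derive them from the unreduced ITT set.
- State that ineligibility for analysis in protocol 10.4 refers to the per-protocol set only. A sentence in the SAP is enough. Editing the protocol itself would need a written amendment or administrative change under protocol 10.3.

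The cost is SAP wording, plus one supplementary table if a per-protocol analysis is wanted. No new data are needed. The trade-off is that the ITT estimate keeps protocol violators and may be slightly less favourable.
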